8.2 Laboratory Assessments Part A and B

Note: Laboratory assessments will be performed at both central and local laboratories, if required.

- **Hematology**: hemoglobin, hematocrit, erythrocyte count (RBCs), thrombocyte count (platelets), leukocyte count (WBCs) with differential in absolute counts (including neutrophils, eosinophils, basophils, lymphocytes, and monocytes)
- **Coagulation**: PT/INR, thrombin time, aPTT, fibrinogen level.
- **Serum Chemistry**: Aspartate aminotransferase (AST), Alanine aminotransferase (ALT), Total, direct, and indirect bilirubin levels, Alkaline phosphatase (ALP), Albumin, Creatinine, Urea, Total Protein, Sodium, Chloride, Calcium, Phosphate, Potassium, Glucose (random), creatine phosphokinase (CPK) and thyroid stimulating hormone (TSH)
- **PK**: Plasma PRN1008 concentration
- **PD**:
 - BTK occupancy in PBMCs at baseline (pre-dose), and 2 and 24 hours after the first dose, then at various times of the day during follow-up visits. For the Day 2 (24 hour) BTK occupancy, PRN1008 should be taken as usual in the evening (only if *bid* dosing) and the PRN1008 morning dose withheld in order to take the blood sample approximately 12 hours after the prior evening dose (for *bid* dosing) or 24 hours after the last dose (for *qd* dosing). Where follow-up is not feasible on Day 2, another day in the first week

of therapy may be used to get trough occupancy instead. For all other visits, occupancy is measured at random times after the usual morning dose.

- Anti-desmoglein-1 and -3 autoantibody titers by enzyme-linked immunosorbent assay (ELISA)
- **Urinalysis:** pH, specific gravity, protein, glucose, ketones, bilirubin, blood, nitrites, urobilinogen and leukocytes measured by dipstick
- **Serology:** HIV, Hepatitis B and Hepatitis C and T-spot TB Test or QuantiFERON® TB testing or QuantiFERON®-TB Gold Plus (QFT Plus) at screening only
- **Pregnancy or FSH:** Serum pregnancy test for women of child bearing potential or serum FSH for post-menopausal females

8.3 Safety and Tolerability Assessments

Specific assessments to evaluate treatment safety include the following: the frequency and type of AEs, clinical laboratory testing, SNAQ appetite questionnaire ([Appendix 6](#)) and vital signs. Patients will remain under observation in the clinic for 2 hours after administration of the first PRN1008 dose and until the PK sample is drawn (see also [Section 12.1](#), Safety Monitoring Committee).

9 STUDY TREATMENT

Part A: Initial PRN1008 dosing will be 400 mg *bid*. The maximum dose in this study, after dose adjustment, will be 600 mg *bid*. Subjects will be treated with PRN1008 for a maximum of 12 weeks.

Patients enrolled in a previous version of this protocol who are still in their 12-week active treatment period with PRN1008 are eligible to continue treatment, initially with their current dose level, under this amended protocol for an additional 12 weeks, i.e. 24 weeks total, following review and signature of the EC approved patient's consent.

Part B: Initial PRN1008 dosing will be 400 mg *qd* unless patients are eligible to roll from Part A to Part B. The maximum dose in this study, after dose adjustment, will be 600 mg *bid*. Subjects will be treated with PRN1008 for a maximum of 24 weeks.

PRN1008 tablets should be taken with a glass of water, with or without food, i.e., a period of fasting is not required.

10 IDENTITY OF INVESTIGATIONAL PRODUCT

10.1 Formulation

Each PRN1008 film-coated tablet contains either 100 mg or 300 mg of PRN1008 drug substance. In addition, the tablet contains Microcrystalline Cellulose (filler), Crospovidone (disintegrant), Sodium Stearyl Fumarate (lubricant) and a non-functional film coating. The 100 mg tablet is a round shape and orange in color. The 300 mg tablet is an oval shape and white in color.

10.2 Packaging

PRN1008 tablets are packaged in white high-density polyethylene (HDPE) bottles with child-resistant induction-sealed caps.

10.3 Storage and Handling

PRN1008 tablets are supplied in white plastic bottles with child-resistant induction-sealed caps or blister packs. The recommended storage condition is 2 to 25°C. Refer to product label for specific instructions.

10.4 Drug Accountability

The Investigator or his/her designated representatives will dispense study drug per the Schedule of Assessments ([Appendix 4](#)).

The Investigator is responsible for the control of drugs under investigation. Adequate records of the receipt (e.g., Drug Receipt Record) and disposition (e.g., Investigational Drug Dispensing Log) of the study drug must be maintained. The investigational Drug Dispensing Log must be kept current and should contain the following information:

- The identification of the participant to whom the study drug was dispensed (for example subject identification number, participant initials, and date of birth)
- The date(s), quantity, and lot number(s) of the study drug dispensed to the participant
- The identification of the person who dispensed the study drug

All records and drug supplies must be available for inspection by the Study Monitor at every monitoring visit. When the study is completed, the Investigator will return any used and unused study drug (e.g., empty, partially used, and unused containers), occluded labels (or the equivalent) to the Sponsor as requested. The completed Drug Dispensing Log and Drug Return Record(s) will be returned to the Local Sponsor. The Investigator's copy of the Drug Return Record(s) must accurately document the return of all study drug supplies to the Sponsor.

10.5 Destruction of Investigational Product

Local or institutional regulations may require immediate destruction of used investigational medicinal product for safety reasons. In these cases, it may be acceptable for investigational study center staff to destroy dispensed investigational product before a monitoring inspection, provided that source document verification is performed on the remaining inventory and reconciled against the documentation of quantity shipped, dispensed, returned, and destroyed, and provided that adequate storage and integrity of drug has been confirmed. Written authorization must be obtained from the Sponsor or Sponsor designee after final accountability prior to destruction.

Unused study drug from the site that has not been stored properly should not be destroyed until the final report has been approved.

Written documentation of destruction must contain the following:

- Identity of investigational product(s) destroyed
- Quantity of investigational product(s) destroyed
- Date of destruction
- Method of destruction
- Name and signature of responsible person who destroyed the investigational products

Investigational sites that do not have a procedure for destruction and appropriate disposal of investigational product, or cannot dispose of investigational product locally may request assistance and documentation for return to the Sponsor, or assignment to a local qualified vendor for destruction and disposal.

11 STATISTICAL METHODS AND DETERMINATION OF SAMPLE SIZE

11.1 Primary Outcome Measures

11.1.1 Safety

The incidence of treatment-emergent AEs (TEAEs), including clinically significant changes in physical examination, laboratory tests, and vital signs.

11.1.2 Efficacy

The proportion of subjects who are able to achieve control of disease activity (CDA) within 4 weeks of starting PRN1008 treatment without the need for doses of prednis(ol)one > 0.5 mg/kg.

11.2 Secondary Outcome Measures

The following clinical activity endpoints* will be assessed:

- Proportion of subjects able to achieve CDA without corticosteroids within 4 weeks
- Proportion of subjects able to achieve a complete response (CR) without corticosteroids within 12 weeks (and 24 weeks in **Part B**)
- Proportion of subjects able to achieve CR without the need for doses of prednis(ol)one of greater than 0.5mg/kg within 12 weeks (and 24 weeks in **Part B**)
- Time to CDA
- Time to CR
- Time to end of consolidation phase
- Time to relapse after PRN1008 treatment discontinuation
- Cumulative corticosteroid usage over the first 12 weeks (and 24 weeks in **Part B**)
- Change from baseline in Pemphigus Disease Area Index (PDAI) and Autoimmune Bullous Skin Disorder Intensity Score (ABSIS) scores at each follow-up visit
- Change from baseline in Autoimmune Bullous Diseases Quality of Life (ABQOL) and Treatment of Autoimmune Bullous Diseases Quality of Life (TABQOL) scores at each follow-up visit
- Change from baseline in appetite (SNAQ score) at each follow-up visit

*Clinical activity endpoints as defined by the EADV 2014 pemphigus S2 guideline ([Hertl et al. 2015](#)) with the exception that CR is defined as CR at a single point in time rather than present for ≥ 2 months

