
Outcome Measures:
	
Primary Outcome Measures:
 
Safety: The incidence of treatment-emergent AEs (TEAEs), including clinically significant changes in physical examination, laboratory tests, and vital signs.
 
Efficacy: The proportion of subjects who are able to achieve control of disease activity (CDA) within 4 weeks of starting PRN1008 treatment without the need for doses of prednis(ol)one > 0.5 mg/kg.
 
Secondary Outcome Measures:*
 
 • Proportion of subjects able to achieve CDA without corticosteroids within 4 weeks • Proportion of subjects able to achieve a complete response (CR) without corticosteroids within 12 weeks (and also 24 weeks in Part B) • Proportion of subjects able to achieve CR without the need for doses of prednis(ol)one of greater than 0.5mg/kg within 12 weeks (and also 24 weeks in Part B) • Time to CDA • Time to CR • Time to end of consolidation phase • Time to relapse after PRN1008 treatment discontinuation • Cumulative corticosteroid usage over the first 12 weeks (and also 24 weeks in Part B) • Change from baseline in Pemphigus Disease Area Index (PDAI) and Autoimmune Bullous Skin Disorder Intensity Score (ABSIS) scores at each follow-up visit • Change from baseline in Autoimmune Bullous Diseases Quality of Life (ABQOL) and Treatment of Autoimmune Bullous Diseases Quality of Life (TABQOL) scores at each follow-up visit • Change from baseline in appetite (SNAQ score) at each follow-up visit 
*Clinical activity endpoints as defined by the EADV 2014 pemphigus S2 guideline (Hertl et al. 2015)
 
Pharmacokinetics Outcome Measure:
 
 • Plasma concentrations of PRN1008 at approximately the time of maximum concentration on Day 1 and at varied subsequent times during outpatient dosing

	
Pharmacodynamic Outcome Measures:
 
 • Percentage BTK occupancy in PBMCs at 2 & 24 hours after the first PRN1008 dose and at various subsequent times during outpatient dosing • Change from baseline in anti-dsg1-3 autoantibody levels by enzyme-linked immunosorbent assay (ELISA) at various time points. 
Exploratory Outcome Measures:
 
Exploratory PK/PD analysis will examine the effects, if any, of covariates on PK and/or PD, and the relationship between PK, PD, and efficacy in this population.

Planned Number of Participants and Interim Analysis:
	

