1.4.2 Experience in Pemphigus Patients in Study PRN1008-005

1.4.2.1 Efficacy

As of January 18, 2018, PRN1008 had been administered to 21 patients with pemphigus (pemphigus vulgaris [PV] and pemphigus foliaceus [PF]), 18 of whom had 4 or more weeks of treatment. Of the 18 patients with efficacy data, 11 (61%) met the primary endpoint of “Control of Disease Activity” (CDA) on a CS dose of ≤ 0.5 mg/kg/day (low-dose CS) by the Week 5 visit. Three patients achieved CDA on no CS (Figure 2). Two patients required high-dose CS temporarily during PRN1008 treatment due to worsening of disease activity. Four patients achieved complete remission (CR) on 1 to 20 mg/day of CS; 3 achieved CR at Week 13 (25%) and one achieved CR at Week 21. Responses were seen in patients with both mild and moderate levels of initial disease (PDAI patient profiles, Figure 3).

Figure 2 PDAI and Clinical Response Patient Profiles of 5 Patients on Zero or Doses of CS ≤ 5 mg

[figure not shown]
[figure not shown]

Figure 3 Timing of Individual Clinical Responses (Day 15 to 29 circled) N=21

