4.3 Secondary Efficacy Endpoints

The secondary efficacy endpoints are:

- 1) Cumulative incidence of patients able to achieve CDA by each visit
- 2) Cumulative incidence of patients able to achieve CDA by each visit on zero steroids.
- 3) Cumulative incidence of patients able to achieve CDA by each visit **with** the need for doses of prednis(ol)one of greater than 0.5 mg/kg
- 4) Cumulative incidence of patients able to achieve CDA by each visit **without** the need for doses of prednis(ol)one of greater than 0.5 mg/kg
- 5) Proportion of patients able to achieve CDA at each visit
- 6) Proportion of patients able to achieve CDA at each visit **with** the need for doses of prednis(ol)one of greater than 0.5 mg/kg
- 7) Proportion of patients able to achieve CDA at each visit **without** the need for doses of prednis(ol)one of greater than 0.5 mg/kg
- 8) Cumulative incidence of patients able to achieve CR by each visit
- 9) Cumulative incidence of patients able to achieve CR by each visit **with** the need for doses of prednis(ol)one of greater than 0.5 mg/kg
- 10) Cumulative incidence of patients able to achieve CR by each visit **without** the need for doses of prednis(ol)one of greater than 0.5 mg/kg
- 11) Proportion of patients able to achieve CR at each visit
- 12) Proportion of patients able to achieve CR at each visit **with** the need for doses of prednis(ol)one of greater than 0.5 mg/kg
- 13) Proportion of patients able to achieve CR at each visit **without** the need for doses of prednis(ol)one of greater than 0.5 mg/kg
- 14) Proportion of patients able to achieve a complete CR **with** the need for dose of prednis(ol)one of greater than 0.5 mg/kg within 24 weeks, i.e. on or prior to Week 25 visit
- 15) Proportion of patients able to achieve a complete response (CR) **without** prednis(ol)one of greater than 0.5 mg/kg within 24 weeks, i.e. on or prior to Week 25 visit

- 16) Time to first CDA
- 17) Time to first CR
- 18) Time to first end of consolidation phase
- 19) Time to first relapse (after CDA has been achieved, as per relapse definition)
- 20) Time to first increase in PDAI
- 21) Cumulative CS usage over 24 weeks
- 22) Change from baseline in Pemphigus Disease Area Index (PDAI) and Autoimmune Bullous Skin Disorder Intensity Score (ABSIS) scores at each visit
- 23) Change from baseline in Autoimmune Bullous Diseases Quality of Life (ABQOL) and Treatment of Autoimmune Bullous Diseases Quality of Life (TABQOL) scores at each visit

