- 24) Change from baseline in appetite (SNAQ score) at each visit

CR, End of consolidation phase, and Relapse definitions are listed below and noted where they differ listed below:

- Complete response (CR): the absence of new or established lesions while the patient is receiving low dose CS, defined in this study as $< \text{ or } = 0.5\text{mg/kg}$ or 0, as stated in the specific endpoint. The duration of CR is not part of the definition for this study.
- End of consolidation phase: The time at which no new lesions have developed for minimum of 2 weeks, approximately 80% of lesions have healed, and when most clinicians start to taper steroids.
- Relapse/flare: Appearance of ≥ 3 new lesions/month that do not heal spontaneously within 1 week, or by extension of established lesions, in a patient who has achieved disease control

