4.7 Changes to Planned Analyses from Protocol

Change	Description	See SAP section
Analysis populations	The following analysis populations are added: 
 ▪ Modified Intent-to-Treat (mITT) Population ▪ Completer Population ▪ Per-Protocol (PP) Population 	3.2.4, 3.2.5, 3.2.6
Secondary endpoints	The secondary endpoints are re-ordered to group all the CDA endpoints together and then followed by the CR endpoints. Some of the endpoints are re-worded for clarity and consistency within the SAP but the meaning and interpretation remained the same as defined in the protocol.	4.3, 5.4.2.1
Additional secondary endpoints	The following secondary efficacy endpoints were not listed in the protocol but included in the Part A SAP. They will be also analyzed for Part B of the study. 
 • Proportion of patients able to achieve CDA at each visit • Proportion of patients able to achieve CDA at each visit with or without the need for doses of prednis(ol)one of greater than 0.5 mg/kg • Cumulative incidence of patients ever achieved CDA by each visit • Cumulative incidence of patients able to achieve CDA by each visit on zero steroids. • Cumulative incidence of patients ever achieved CDA by each visit with or without the need for doses of prednis(ol)one of greater than 0.5 mg/kg • Proportion of patients able to achieve CR at each visit • Proportion of patients able to achieve CR at each visit with or without the need for doses of prednis(ol)one of greater than 0.5 mg/kg • Cumulative incidence of patients ever achieved CR by each visit 	4.3

	
• Cumulative incidence of patients ever achieved CR by each visit with or without the need for doses of prednis(ol)one of greater than 0.5 mg/kg• Time to first increase in PDAI	
--	---	--

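### The Part B SAP omits the protocol's secondary endpoint of complete response without corticosteroids and does not declare the omission

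*Protocol*

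**What the plan says.** Protocol 11.2 lists "Proportion of subjects able to achieve a complete response (CR) without corticosteroids within 12 weeks" and adds 24 weeks for Part B. The synopsis carries the same item. In both places the next bullet is a different endpoint: CR without prednis(ol)one above 0.5 mg/kg over the same periods.

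The Part A SAP keeps the steroid-free endpoint. It has its own section (8.2.2) and its own tables (14.2.2.2.1 to 14.2.2.2.3).

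The Part B SAP, section 4.3, lists 24 secondary endpoints. Its only zero-steroid response item concerns CDA: "Cumulative incidence of patients able to achieve CDA by each visit on zero steroids". Its 24-week CR items (14 and 15) are set at "prednis(ol)one of greater than 0.5 mg/kg within 24 weeks, i.e. on or prior to Week 25 visit", not at zero. Below the list, CR is defined on a steroid dose of at most 0.5 mg/kg "or 0, as stated in the specific endpoint".

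Part B SAP 4.7 records added populations, re-ordering, re-wording and added endpoints. It says that some endpoints were "re-worded for clarity and consistency within the SAP but the meaning and interpretation remained the same as defined in the protocol". No removal is recorded.

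**The concern.** Part B is open-label with no control arm, and patients may enter on low-dose corticosteroid or be given rescue steroid. CR with no steroid is therefore the CR measure least confounded by background treatment.

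It is also the one whose meaning travels best between the two Parts. Part A SAP 3.2.3 ties CR to 10 mg/day of prednisolone or less. Part B SAP 3.4.7 allows any steroid dose, while Part B SAP 4.3 says 0.5 mg/kg or less, or zero. The protocol plans to combine the Parts where appropriate.

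If the Part B SAP is followed as written, the Part B report gives no rate and no interval for this endpoint. A reader who relies on 4.7 to find departures from the protocol would not learn that it is missing.

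**Working it through.** **Design figure, for context only.** The plan's precision statement reproduces: 1.2816 × √(0.5 × 0.5 / 25) = 0.128, stated as ±13 points. The point below does not depend on it.

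**Protocol against the two SAPs**

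| Protocol 11.2 response endpoint | Part A SAP | Part B SAP |
|---|---|---|
| CDA, no steroid, 4 weeks | 8.2.1 | item 2, read at Week 5 |
| CR, no steroid, 12 weeks (24 in Part B) | 8.2.2 | none |
| CR, no prednis(ol)one above 0.5 mg/kg, 12 weeks (24 in Part B) | 8.2.3 | item 10 at Week 13; item 15 at Week 25 |

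**Count of the Part B response items (4.3, repeated in 5.4.2.1)**

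| Steroid condition | CDA items | CR items |
|---|---|---|
| Any dose | 1, 5 | 8, 11 |
| Zero | 2 | none |
| With more than 0.5 mg/kg | 3, 6 | 9, 12, 14 |
| Without more than 0.5 mg/kg | 4, 7 | 10, 13, 15 |
| Total | 7 | 8 |

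The shells follow the same pattern. Tables B.14.2.2.2.1 to B.14.2.2.2.3 cover CDA with no corticosteroid. Tables B.14.2.2.8 to B.14.2.2.15 cover CR, and none is restricted to zero steroids. The SAP text withheld from the public copy lies between 3.2.7 and 3.4, outside the endpoint sections, so it does not explain the gap.

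**Internal check.** The CR definition in 4.3 relies on individual endpoints to say when the dose must be zero. No CR endpoint says so. The Part B SAP is therefore incomplete on its own terms.

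**Why the retained endpoint is not a substitute.** Under one look-back rule, steroid-free CR is a subset of CR without more than 0.5 mg/kg. The retained rate is only an upper bound: the steroid-free rate may be anything from zero up to it.

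The Part A data in Protocol 1.4.2.1, as of 18 January 2018, illustrate this: "Four patients achieved complete remission (CR) on 1 to 20 mg/day of CS". On those doses alone, none of the four was steroid-free. A dose of 20 mg/day is within 0.5 mg/kg for anyone weighing at least 20 / 0.5 = 40 kg. One of the four occurred at Week 21, outside the 12-week window. These data show that the two versions can differ; they do not predict Part B.

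**A zero count would still be informative.** With the planned 25 patients and 0 responders, the exact upper limits are:

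- 80% interval: 1 − 0.10^(1/25) = 8.8%
- 95% interval: 1 − 0.025^(1/25) = 13.7%

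The mITT population may be smaller than 25, and the limits would then be wider.

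**The case against.** The best defence is that the information is not lost. Listing B.16.2.6.10 puts CR status beside the steroid dose on the day before each visit. Tables B.14.2.2.27 and B.14.2.2.28 summarise steroid dose in patients with at least one CR. Listings B.16.2.6.1 and B.16.2.6.9 give response dates and steroid start and stop dates. Part B also plans no hypothesis tests. This stands in part: a count could be made afterwards. However, the day-before dose alone does not show that no steroid was taken before CR, and no pre-specified proportion or interval is planned.

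A second defence concerns versions. Part B SAP section 1 cites protocol version 7.0, section 2.5 calls 6.0 current, and the supplied protocol refers to amendment 5.0 (1.4) and Version 5 (Appendix 4). Which version was supplied cannot be confirmed. That is a fair caveat, but the unfulfilled reference to zero in the SAP's own CR definition does not depend on it.

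Three stronger readings are tempting, and the documents do not support them:

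- **That the endpoint was dropped because of the results.** The Part A SAP is dated 06-Jan-2019, after the January 2018 data and the August 2018 interim report, and it keeps the endpoint.
- **That only the more favourable CR results can be reported.** The listings and tables above show steroid dose alongside CR.
- **That the sentence in 4.7 is false.** That "the meaning and interpretation remained the same as defined in the protocol" is said of re-worded endpoints; it does not claim that none was removed. The fault is an omission from the list.

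**Conclusion.** The Part B SAP is wrong as written on this point. One protocol secondary endpoint, at two time points (12 and 24 weeks), has no Part B analysis, and the section that records changes does not say so. Zero of eight CR response items cover it. A drafting slip is the likeliest explanation, because the CR definition still makes room for a zero-dose endpoint.

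The omission is confined to Part B; Part A analyses the 12-week version. The effect on the reported CR rate cannot be calculated from the plan. The conclusion assumes that the endpoint list in the supplied protocol is the one the SAP was meant to implement. Because the endpoint is secondary and descriptive and can be restored cheaply, this should be corrected, but it does not undermine the primary analysis.

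**What to change.** Add to Part B SAP 4.3, 5.4.2.1 and the shells the cumulative incidence of CR on zero systemic corticosteroids by visit. Mark Week 13 and Week 25 as the protocol time points, give exact (Clopper-Pearson) 80% and 95% intervals, and present it for the mITT, Completer and PP populations.

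State the look-back rule, since it changes who counts:

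- **Main analysis:** the Part A 8.2.2 rule, with no systemic corticosteroid from treatment start to first CR, for comparability between Parts. Patients who enter on steroid, whose regimen Protocol 6.3.2 says to maintain for the first two weeks, will almost automatically be non-responders. Report how many there are.
- **Optional supplement:** a day-before rule, as used for the Part B primary endpoint (5.4.1). It would count a patient just tapered off steroid, so it is less free of background treatment.

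If the endpoint was dropped on purpose, declare and justify that in 4.7.

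The cost is one table shell repeated for three populations. Steroid records are already collected, and 5.4.2.3 already converts them to prednisone equivalents, so no new data are needed.
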